7.1.3. Best Spectacle Corrected Visual Acuity (BSCVA) and Corrected Visual Acuity

The actual value and change from baseline in number of letters correct will be calculated for each post-baseline visit and summarized as continuous variable by treatment group. If a subject has both BSCVA and Corrected VA data at a specific visit, BSCVA data will be used in calculation of the change from baseline value.

The number and percentage of subjects in each category will be presented. Similar analyses on change in number of letters correct from baseline will be conducted by visit.

7.1.4. Slit Lamp Examination

The slit lamp examination will include the measurement of aqueous cell and flare by a standard grading system and an evaluation for the presence of corneal abnormalities, pupillary

irregularities, and iris pigmentation. Crystalline lens status (for phakic subjects) will also be assessed. Slit lamp examination will be performed for both the study eye and the fellow eye at each scheduled visit except the surgery day. Severity grades for the findings are:

For the evaluation of anterior chamber cells, anterior chamber depth and flare, the following grading schemes are used:

The frequency distribution for the severity grade at each scheduled visit will be summarized by treatment group for the study eye.

Slit lamp examination will be presented in a data listing.

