### 9.4 Safety Analyses

No formal statistical testing will be conducted for the safety analyses. No imputation will be performed for the missing values. All summaries will be based on the available data of the safety population.

Descriptive statistics will be calculated as described in Section 9.3 at each visit for the 3 treatment groups separately. For each reported adverse event in each treatment group, the percentage of eyes will be reported. The sections below describe specific data handling for adverse events, and best spectacle corrected visual acuity (BSCVA).

Other safety outcomes such as slit lamp examination, intraocular pressure, dilated fundus examination, and endothelial cell count (from specular microscopy at selected sites) will be summarized descriptively at each visit for

| CLINICAL PROTOCOL |               |               |
|-------------------|---------------|---------------|
| Date:             | Phase:        | Protocol No.: |
| June 06, 2022     | Phase 3 Study | GC-010        |

the Safety Population. Line listings for abnormal findings for individual eyes may be provided. A line listing of non-ocular serious adverse events will be provided by subject.

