2.3. Assessment Schedule

2.4. Sample Size Determination

In order to detect adverse events that occur at a rate of 1% or higher, safety in the clinical program will be demonstrated in a minimum of 300 subjects who have completed the expected duration of drug elution from either implant model.

3. Analysis Sets

Intent to Treat Analysis Set (ITT)

This analysis set includes all subjects who are randomized.

Per-Protocol Analysis Set (PP)

The Per-Protocol analysis set is a subset of the ITT analysis set. It includes all the ITT subjects who received the study treatment based on the randomization schedule and do not have major protocol deviations likely to impact the primary efficacy endpoints.

Safety Analysis Set

The safety analysis set will contain all subjects who are randomized and receive at least one dose of study treatment. Subjects will be grouped according to their actual treatment received,

4. General Statistical Considerations

Continuous data will be summarized with the number of non-missing values, mean, standard deviation, minimum, median, and maximum. Other selected percentiles, such as the 25th percentile and 75th percentile may be presented for parameters that are not normally distributed or are suspected of exhibiting that tendency. Categorical data will be summarized with the number of non-missing values and the numbers of values equal to each of the possible values. Percentages of subjects with each of the possible values will be calculated from the number of subjects in the relevant cohort of the corresponding analysis set, unless stated otherwise. Some continuous variables may also be grouped into categorical levels and evaluated in frequency tables.

All inferential statistical analyses will be performed with a two-sided confidence level of 95% or a two-sided significance level of 0.05, except when stated otherwise using SAS[®] software, Version 9.4, or higher.

Data displays produced for this study will include three types: summary tables, data listings, and figures.

Data listings will simply list the data recorded on the case report form (CRF) or derived for each subject. They will be ordered by treatment, subject number, study eye, and time of assessment. Additional levels of ordering may be employed as appropriate. Data listings will not display subject initials.

In general, summary tables will be presented by treatment group:

- Implant
- Implant
- Sham/Timolol

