4.3. Adjustment for Covariates

4.4. Handling Missing Data

4.4.1. Handling of Missing Data/Intercurrent Events for Efficacy Variables

Please see section 6.1.3 for handling missing IOP data/intercurrent events for the primary analysis.

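### In the readable SAP 7.1.4, lens status is summarised only visit by visit, so study eyes whose lens is removed have no later lens grade and lens worsening can be understated

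*SAP*

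**What the plan says.** SAP 7.1.4 describes the slit-lamp examination and says of the lens: "Crystalline lens status (for phakic subjects) will also be assessed". The planned summary is "The frequency distribution for the severity grade at each scheduled visit will be summarized by treatment group for the study eye", supplemented by a listing: "Slit lamp examination will be presented in a data listing". The section introduces its scale with "Severity grades for the findings are", but the scale itself is missing from the public copy.

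Protocol 9.4 governs missing safety data: "No imputation will be performed for the missing values", and "All summaries will be based on the available data of the safety population". SAP Section 4 gives the general denominator rule, which refers to the analysis set concerned: "Percentages of subjects with each of the possible values will be calculated from the number of subjects in the relevant cohort of the corresponding analysis". The readable text does not say what the relevant cohort is for lens status.

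The readable handling of intercurrent events concerns efficacy. SAP 4.4.1 says "Please see section 6.1.3 for handling missing IOP data/intercurrent events for the primary analysis". SAP 5.5 provides later ocular procedures in the study eye as a listing only.

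Several other safety measures have a cumulative summary as well as, or instead of, a by-visit one:

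- implant position at any visit (SAP 7.1.5)
- clinically significant ophthalmoscopy findings at any post-baseline visit (7.1.6)
- largest change in vertical cup-to-disc ratio (7.1.8)
- endothelial cell loss of at least 30% overall (7.1.10)

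The readable part of 7.1.4 has none.

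**The concern.** For the lens, a bad outcome can end its own measurement. Once the lens is removed, the eye is no longer phakic and cannot contribute a lens grade at later visits. With available-data summaries and no stated rule for such eyes, the natural reading is that they leave the lens table. If eyes with worse lenses are more likely to be operated on, the remaining eyes are a favourable selection, and the selection can grow over 36 months.

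A by-visit comparison between arms then depends on how many lenses were removed in each arm as well as on how many worsened. Removal could differ by arm: Protocol 7.3.5.1 has the surgeon perform the implantation or the sham according to assignment, and Protocol Section 11 masks the subject and the staff who make certain measurements. At least one clinician per site therefore knows the treatment. The documents do not say whether or how far this affects later surgery.

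At stake is the readability of one long-term safety comparison between the implant arms and control.

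**Working it through.** The documents state no lens, cataract or lens-removal figure, so there is nothing of the plan's own to reproduce. The following is an illustration.

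**Inputs**

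- Subjects per arm: about 186 (Protocol synopsis, Power and Sample Size). Used only to show counts, taking all study eyes as phakic at baseline. The percentages do not depend on this.
- c: share of baseline-phakic study eyes with lens worsening by the visit. Assumed 20% or 10%.
- s: share of those worsened eyes whose lens is removed before the visit. Assumed 25%, 50% or 75%.
- No removal among eyes that have not worsened (assumed).

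**Formula.** With currently phakic eyes as denominator, the table shows c(1 − s)/(1 − cs).

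| c | s = 25% | s = 50% | s = 75% |
|---|---|---|---|
| 20% | 0.15/0.95 = 15.8% | 0.10/0.90 = 11.1% | 0.05/0.85 = 5.9% |
| 10% | 0.075/0.975 = 7.7% | 0.05/0.95 = 5.3% | 0.025/0.925 = 2.7% |

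**Equal true rates, unequal removal.** True 20% in both arms means 0.20 × 186 = 37.2 worsened eyes per arm.

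- Removal of 50% takes out 18.6 and leaves 18.6/(186 − 18.6) = 11.1%.
- Removal of 25% takes out 9.3 and leaves 27.9/(186 − 9.3) = 15.8%.

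The arm with more surgery looks better although the arms are the same.

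**Unequal true rates.**

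- True 20% versus 10%, removal 25% in both: 15.8% versus 7.7%. The order is kept.
- True 20% versus 10%, removal 75% versus 25%: 5.9% versus 7.7%. The order is reversed.
- Break-even with 25% removal in the 10% arm: 0.2(1 − s)/(1 − 0.2s) = 0.0769 gives s of about 67%. With no removal in the 10% arm, 0.2(1 − s)/(1 − 0.2s) = 0.10 gives s of about 56%.

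**Does the denominator matter?** If all baseline-phakic eyes are the denominator but removed lenses are not counted as events, the table shows c(1 − s). The 50% versus 25% case becomes 10.0% versus 15.0%, nearly the same distortion.

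**Does selectivity matter?** If a share u of unworsened eyes is also removed, the table shows c(1 − s)/[c(1 − s) + (1 − c)(1 − u)]. With u = s this equals c, so there is no bias. The understatement needs worsened eyes to be removed more often than unworsened ones.

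**With removal counted as an event** over all baseline-phakic eyes, and u = 0, the result is [c(1 − s) + cs] = c whatever s is.

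**The case against.** The sentence on phakic subjects says who is examined, and a lens can be assessed only where there is one. It does not define the table's denominator. The text after the grading introductions is missing from the public copy, and the SAP introduction says that table shells are in a separate document. So a lens scale, or a category for a removed lens, may exist unseen. This stands, and the point is limited to the readable text.

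Cataract also has another route into the report. Under Protocol Section 10, new conditions and unexpected worsening of existing ones are adverse events. SAP 7.1.2 tabulates ocular events by arm, with severity and relationship, and a subject counted there stays counted after surgery. This is a real mitigation, but incomplete. The same protocol section excludes changes that fit the natural course of a chronic condition, and does not count procedures themselves as events. A lens opacity present at baseline that progresses to surgery may therefore be absent from those tables, leaving the surgery visible only in a listing.

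Two stronger readings are tempting. A reader might infer that the lens grade necessarily looks better in the arm with more cataract surgery. The documents do not support that: the effect depends on selective and unequal removal, which they do not quantify, and the examples above include cases where the order is kept. A reader might also infer that acuity data in SAP 7.1.3 should be set aside after lens removal. That would condition on the same post-randomisation event and drop the eyes with the worst lenses, so it is not recommended.

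**Conclusion.** The point holds as a gap in the readable SAP. Eyes that lose the lens have no later grade, and no visible rule, category or cumulative summary keeps them in view. The by-visit table can then understate lens worsening, for example showing 15.8%, 11.1% or 5.9% for a true 20%. It can mislead between arms if removal differs. Reversing a true 20% versus 10% takes a large imbalance, about 67% versus 25% of worsened eyes removed.

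All these rates are assumptions, and the direction of the bias rests on worsened eyes being operated on preferentially. That lens status is graded, and that only currently phakic eyes are tabulated, are inferences from the readable text. The measure is descriptive: no safety testing is planned, and no primary or key secondary endpoint is affected. It is an inexpensive improvement, not a flaw in the trial's main conclusions.

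**What to change.** In SAP 7.1.4, next to the by-visit table, add a summary for study eyes phakic at baseline: the number and percentage by arm with lens-grade worsening or lens removal at any post-baseline time. Use all such eyes as the denominator and show lens removal as a separate row, so that a reader can see how much of the composite is surgery. If the unpublished grade definitions or table shells already do this, a cross-reference in 7.1.4 is enough.

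No new data collection appears necessary. The slit-lamp examination includes the crystalline lens (Protocol 7.3.4.1, SAP 7.1.4), and procedures in the study eye are captured for the SAP 5.5 listing. This presumes that the lens data are recorded on a scale that allows worsening to be defined. The cost is one extra table and a higher reported lens-event rate in every arm, because lens removals for any reason would now be counted.

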7.1.5. Gonioscopy and Implant Visibility Assessment

Gonioscopy will be used to assess angle abnormalities including presence of goniosynechiae, angle anatomy and implant location (in eyes with implants) for both the study eye and fellow eye at Screening, Day 10, Weeks 4, 6, and Months 3, 6, 12, 18, 24, 30, and 36. The Shaffer angle grade will be collected only at screening visit for eligibility criteria.

The number and percentage of subjects in each category will be summarized for the study eye.

Gonioscopy findings include abnormal anatomy, goniosynechiae, rubeosis, and other angle abnormalities. The number and percentage of subjects with the gonioscopy findings at each scheduled visit will be summarized by treatment group for the study eye.

The implant visibility assessment will be performed during gonioscopy examination. The number and percentage of subjects with implant location not in original position, or implant being anchored but migrated at any visit will be summarized by treatment group.

Gonioscopy and implant visibility assessment will be presented in data listings.

7.1.6. Ophthalmoscopy

Ophthalmoscopy will be performed with pupil dilation to examine the fundus and nerve abnormalities for the study eye at Screening, Months 3, 6, 9, 12, 15, 18, 21, 24, 27, 30, 33, and 36. The dilated fundus exam will include evaluation of the macula and vessels as well as peripheral fundus examination.

In addition, the number and percentage of subjects with any clinically significant findings at any post-baseline visits, and at each scheduled post-baseline visit will be also presented by treatment group.

7.1.7. Visual Field

Visual fields will be obtained at Screening, Months 6, 12, 18, 24, 30, and 36.

The same test methodology must be used throughout the entire study for a given subject. Visual field mean deviation (MD) will be recorded in decibels (dB). The actual value and change from baseline in MD be calculated for each post-baseline visit and summarized as continuous variable by treatment group.

7.1.8. Vertical Cup-to-Disc Ratio

The cup-to-disc (C/D) ratio is a numerical expression indicating the percentage of disc occupied by the optic cup. Vertical C/D ratio will be assessed, and a score from 0.1 to 0.9 (in 0.1 increments) will be recorded for the study eye at Screening, and Months 6, 12, 18, 24, 30, and 36. The change from baseline in C/D ratio at each follow-up visit will be categorized as:

The actual value and change from baseline in vertical C/D ratio for the study eye will be calculated for each post-baseline visit and summarized as continuous variable by treatment group.

The number and percentage of subjects in each category listed above will be provided by treatment group for the study eye as overall (i.e., based on the maximum change from baseline across any post-baseline visits), and by visit.

7.1.9. Pachymetry

Pachymetry is performed to determine corneal thickness for the study eye at Screening, and Months 12, 24, and 36. For each evaluation, three measurements are to be taken utilizing an ultrasonic pachymeter and the mean recorded for analysis. The actual value and change from baseline in corneal thickness will be calculated for each post-baseline visit and summarized by treatment group.

7.1.10. Specular Microscopy

Specular microscopy will be only captured at selected sites. Specular microscopic central image will be taken in the study eye at Screening, Month 3, Months 12, 24 and 36. Endothelial cell density, percent hexagonality, and the coefficient of variation (COV) will be assessed from calibrated specular microscope images. At each examination, average endothelial cell density for each eye will be reported by the reading center and used for analysis.

The actual, change from baseline, and percent change from baseline in central endothelial cell density will be calculated for each post-baseline visit and summarized by treatment group.

In addition, the number and percentage of subjects with \geq 30% loss from baseline in central endothelial cell density will be summarized by treatment group for study eye as overall (i.e., based on the minimum change from baseline across any post-baseline visits), and by visit.

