### 6 MATERIALS

### 6.1 Study Medications

Subjects randomized to the implant groups in the study will undergo surgery to receive the implants using the test articles described below in Section 6.1.1, befor

Subjects randomized to the control group will undergo a sham procedure (pretend surgery) using a needleless syringe (as described in Section 6.1.4, Other Articles: Sham Procedure) before

During the study period, bottles of study medication will be dispensed to all subjects at Visit 3 (Operative Day 0), Visit 8 (Month 3),

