# 4) Measure best spectacle corrected visual acuity through manifest refraction (ETDRS).

- 5) Conduct slit-lamp biomicroscopy & ocular assessments (conjunctiva and iris).
- 6) Specular microscopy photos will be captured at selected sites at any time during this visit (recommended prior to topical anesthetic).
- Measure diurnal IOP at 8:00 AM (± 30 minutes) using the two-person methodology.
- Measure diurnal IOP at 10:00 AM (± 30 minutes) using the two-person methodology.
- Measure diurnal IOP at 4:00 PM (± 30 minutes) using the two-person methodology.
- 10) A pregnancy test (if applicable) may be administered at any time during this visit. Urine pregnancy test is acceptable.
- 11) Verify eligibility against all study inclusion and exclusion criteria.
- 12) Designate the qualifying eye as the study eye. If both eyes qualify, select the RIGHT eye. Subjects will be treated unilaterally, only one eye will go through the study treatment. The fellow eye will be treated outside the parameters of the study per investigator discretion using their standard of care options.

| CLINICAL PROTOCOL |                            |        |
|-------------------|----------------------------|--------|
| Date:             | Date: Phase: Protocol No.: |        |
| June 06, 2022     | Phase 3 Study              | GC-010 |

If the subject is ineligible for the study, complete the appropriate CRF.

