4.1. Definition of Variables

4.1.1. Baseline

Baseline for analysis purposes is defined as the last assessment prior to treatment start date/time.

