4.1.2. Change and Percent Change from Baseline

• Change from baseline is defined as the post baseline value minus the baseline value.

For standard IOP, the post-baseline collection time will be mapped in order to calculate the change from baseline value.

• Percent change from baseline is calculated as follows: Percent change = (Change from baseline / Baseline) * 100.

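### The overall count of eyes with at least 30% endothelial cell loss can miss eyes whose later images become unreadable, and no within-eye change from Month 3 is planned

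*SAP*

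**What the plan says.** The endothelial analysis is in SAP 7.1.10 and applies to selected sites only.

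- Schedule: "Specular microscopic central image will be taken in the study eye at Screening, Month 3, Months 12, 24 and 36". Protocol 7.3.4.2 instead places the pre-surgery image at Visit 2 (Baseline): "Specular microscopy photos will be captured at selected sites at any time during this visit". Both precede surgery, so this mismatch does not affect the point.
- Value analysed: "average endothelial cell density for each eye will be reported by the reading center and used for analysis". The readable text of the section has no category for an unreadable image, a decompensated cornea or a grafted eye.
- Reference: "Baseline for analysis purposes is defined as the last assessment prior to treatment start date/time" (SAP 4.1.1), which here means the pre-surgery image.
- Sign: "Change from baseline is defined as the post baseline value minus the baseline value" (SAP 4.1.2). The minimum is therefore the largest loss, which is the right direction.
- Large-loss count: eyes losing 30% or more, "as overall (i.e., based on the minimum change from baseline across any post-baseline visits), and by visit".
- By-visit summaries: actual value, change and percent change from baseline, by arm.
- Missing safety data: "No imputation will be performed for the missing values" (Protocol 9.4). The readable SAP text sets no different rule for safety values.
- Denominator: SAP section 4 takes percentages over the subjects in the relevant cohort of the analysis set, whereas Protocol 9.4 uses available data. The SAP introduction says that its definitions supersede the protocol's, but 7.1.10 does not state a denominator for this row.
- Control: Protocol 6.1 gives the control arm a "sham procedure (pretend surgery) using a needleless syringe", so only the implant arms have intraocular surgery.

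**The concern.** For an implant followed for three years, two endothelial questions matter: how many eyes lose a large share of their cells, and whether loss continues after the early postoperative period.

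The overall row answers the first from the images that could be read. If a cornea becomes too oedematous for cells to be counted, no density is reported, and the eye is classified by its earlier, better images. The same happens after a graft if no density is reported. If a post-graft density is reported, nothing in the section excludes it, although it no longer describes the subject's own endothelium. Either way, the eyes that fare worst can fall on the favourable side of the count.

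For the second question, every planned change refers back to the pre-surgery image. The by-visit rows help, but each rests on the eyes imaged at that visit, so a difference between two rows mixes change within eyes with a change in which eyes are included.

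The project team is unmasked at the Month 12 lock (SAP introduction), so a classification rule is best written before then.

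**Working it through.** The plan states no size or expected rate for this analysis, so there is no figure to reproduce. I trace the written rules through cases with assumed values.

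**1. One eye under the overall rule.** Assume changes of -12% at Month 3 and -24% at Month 12, then no readable image at Months 24 and 36. The minimum over reported values is min(-12, -24) = -24%. This does not reach -30%, so the eye is classed as not having large loss. Because it has post-baseline densities, it stays in the denominator under either denominator rule.

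**2. Effect on the rate.** Per arm, let m = eyes at specular sites, k = eyes with at least 30% loss on readable images, and u = decompensated eyes not counted. The possible rates are:

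- k/m: the uncounted eyes stay in the denominator (as in step 1, or under the SAP cohort rule);
- k/(m - u): they drop out (available-data rule, for a single visit or for eyes with no post-baseline density);
- (k + u)/m: they are counted as large loss.

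With k = u = 2:

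| m (assumed) | k/m | k/(m - u) | (k + u)/m |
|---|---|---|---|
| 30 | 6.7% | 7.1% | 13.3% |
| 60 | 3.3% | 3.4% | 6.7% |
| 100 | 2.0% | 2.0% | 4.0% |
| 186 | 1.1% | 1.1% | 2.2% |

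The last line would require every randomized eye in the arm to be imaged, so it is a limit. Each uncounted eye moves k/m by 1/m: 3.3, 1.7, 1.0 or 0.5 percentage points.

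Choosing a denominator does not remove the gap. k/(m - u) < (k + u)/m is equivalent to u(m - k - u) > 0, which holds whenever u > 0 and at least one eye is readable without large loss.

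**3. Early versus later loss.** Take two assumed courses at Months 3, 12, 24 and 36:

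- one-off: -32, -32, -32, -32%;
- continuing: -3, -10, -21, -32%.

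Both have a minimum of -32% and count the same in the overall row. The by-visit rows differ (-32% against -3% at Month 3). The within-eye change from Month 3 to Month 36 is 0.68/0.68 - 1 = 0.0% for the first and 0.68/0.97 - 1 = -29.9% for the second.

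**4. Changing set of eyes.** Assume 100 imaged eyes: 98 at -4% throughout, and two that follow step 1.

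- Month 3 mean: (98 × -4 + 2 × -12)/100 = -4.16%.
- Month 12 mean: (98 × -4 + 2 × -24)/100 = -4.40%.
- Month 24 mean: (98 × -4)/98 = -4.00%.

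The mean appears to recover between Months 12 and 24, although no eye recovered.

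**The case against.** A reader might infer that corneal decompensation disappears from the safety report. The documents do not support that. It should appear among adverse events (SAP 7.1.2), with sight-threatening events serious under Protocol 10.1, and in slit-lamp corneal findings (SAP 7.1.4), pachymetry at Months 12, 24 and 36 (7.1.9) and visual acuity (7.1.3). A graft would be in the listing of ocular procedures (5.5). What remains is that none of these corrects the large-loss rate.

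A reader might also infer that surgical loss cannot be told from continuing loss. That too goes too far. The by-visit changes include Month 3, and the sham arm is a no-implant reference at each imaging visit, so early and later loss can be compared at group level. With the same eyes at each visit, the difference in means equals the mean within-eye change in percentage points of baseline. Only changing membership breaks this. Nor do the documents show that surgical loss is complete by Month 3.

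A third tempting reading is that every unreadable eye counts as free of large loss, and that the bias always hides harm. For by-visit percentages, and for eyes with no post-baseline image, the result depends on the denominator. Ordinary dropout of unaffected eyes would raise an available-data rate. The classification is definite only for the overall row and for an eye with earlier readings short of 30% loss.

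Two further points are fair. SAP section 4 shows the number of non-missing values, so a gap would be visible, though not its reason. Table shells are in a separate document, so image-status rows cannot be assumed absent. Finally, replacing the main count would label transient oedema as permanent loss, so a supplementary count is the proportionate remedy. The plan already has a comparable convention on the efficacy side: SAP 6.1.3 treats missing data as non-response in the responder analyses.

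**Conclusion.** The point holds in a limited form, as a cheap improvement. As written, the overall row classes an eye as not having large loss when its earlier readings fall short of 30% loss and its later images are unreadable because of decompensation or a graft. The row can therefore understate large loss. Separately, early and later loss are visible at group level but not within eyes.

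The size is unknown. The documents give no imaged number, unreadable-image rate or decompensation rate, and the number of affected eyes may be zero. If as many such eyes exist as counted ones, the reported rate is about half of what it would be with them included: 2.0% against 4.0% at 100 eyes, 6.7% against 13.3% at 30. All sizes and courses in the working are illustrative, and they assume that a decompensated cornea yields no countable image.

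**What to change.** In SAP 7.1.10:

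1. Keep the measured count of eyes with at least 30% loss, and state its denominator, overall and by visit.
2. Add a supplementary count that also classes as large loss any study eye at a specular site (a) whose image is missing or unreadable because of corneal decompensation, unless a later readable image shows less than 30% loss, or (b) that has had a corneal graft. Exclude post-graft densities.
3. Tabulate missing or unreadable images by arm, visit and reason.
4. Add the paired within-eye percent change from Month 3 to Months 12, 24 and 36, by arm, with a 95% CI and the number of pairs. Describe it as change after Month 3, not as proven non-surgical loss. The interval is descriptive, in keeping with the absence of formal safety testing in Protocol 9.4. Pairing removes the changing set of eyes but still omits unreadable ones, so items 2 and 3 are needed beside it.

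No new visits or images are required. The cost is SAP wording, a few table rows, and recording why an image is missing, which the documents do not show being collected. The supplementary rate may be slightly higher than the measured one.
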